17.4. SNELLEN EQUIVALENCE (VISUAL ACUITY CONVERSION CHART)

Line Number	Visual Angle (min)	Spatial Frequency (Cyc/deg)	LogMAR	Distance				Near					
				% Central Visual Efficiency	Snellen Equivalent			% Central Visual Efficiency	Inches (14/)	Centimeters (35/)	Revised Jaeger Standard	American Point-Type	"M" Notation
					Feet 20/	Meter 6/	Decimal						
-3	0.50	60.00	0.30	100	10	3.0	2.00	100	7.0	17.5	-	-	0.20
-2	0.63	48.00	0.20	100	12.5	3.8	1.60	100	8.8	21.9	-	-	0.25
-1	0.80	37.50	0.10	100	16	4.8	1.25	100	11.2	28.0	-	-	0.32
0	1.00	30.00	0.00	100	20	6.0	1.00	100	14.0	35.0	1	3	0.40
1	1.25	24.00	-0.10	95	25	7.5	0.80	100	17.5	43.8	2	4	0.50
-	1.50	20.00	-0.18	91	30	9.0	0.67	95	21.0	52.5	3	5	0.60
2	1.60	18.75	-0.20	90	32	9.6	0.63	94	22.4	56.0	4	6	0.64
3	2.00	15.00	-0.30	85	40	12.0	0.50	90	28.0	70.0	5	7	0.80
4	2.50	12.00	-0.40	75	50	15.0	0.40	50	35.0	87.5	6	8	1.0
-	3.00	10.00	-0.48	67	60	18.0	0.33	42	42.0	105.0	7	9	1.2
5	3.15	9.52	-0.50	65	63	18.9	0.32	40	44.1	110.3	8	10	1.3
-	3.50	8.57	-0.54	63	70	21.0	0.29	32	49.0	122.5	-	-	1.4
6	4.00	7.50	-0.60	60	80	24.0	0.25	20	56.0	140.0	9	11	1.6
7	5.00	6.00	-0.70	50	100	30.0	0.20	15	70.0	175.0	10	12	2.0
-	5.70	5.26	-0.76	44	114	34.2	0.18	12	79.8	199.5	11	13	2.3
8	6.25	4.80	-0.80	40	125	37.5	0.16	10	87.5	218.8	12	14	2.5
-	7.50	4.00	-0.88	32	150	45.0	0.13	6	105.0	262.5	-	-	3.0
9	8.00	3.75	-0.90	30	160	48.0	0.13	5	112.0	280.0	13	21	3.2
10	10.00	3.00	-1.00	20	200	60.0	0.10	2	140.0	350.0	14	23	4.0
11	12.50	2.40	-1.10	17	250	75.0	0.08	0	175.0	437.5	-	-	5.0
-	15.00	2.00	-1.18	16	300	90.0	0.07	0	210.0	525.0	-	-	6.0
12	16.00	1.88	-1.20	15	320	96.0	0.06	0	224.0	560.0	-	-	6.4
13	20.00	1.50	-1.30	10	400	120.0	0.05	0	280.0	700.0	-	-	8.0
16	40.00	0.75	-1.60	5	800	240.0	0.03	0	560.0	1400.0	-	-	16.0
20	100.00	0.30	-2.00	0	2000'	600.0	0.01	0	1400.0	3500.0	-	-	40.0
30	1000.00	0.03	-3.00	0	20000'	6000.0	0.001	0	14000.0	35000.0	-	-	400.0

Bold values are standard logMAR progression.
 LogMAR = logarithm of the minimum angle of resolution
 *20/2000 is equivalent to counting fingers @ 2 feet
 †20/20000 is equivalent to hand motion @ 2 feet

17.5. LIST OF CONCOMITANT MEDICATIONS

The following lists are not necessarily exhaustive lists of every possible substrate/inhibitor/inducer.

Table A: List of CYP450 Substrates to be Used With Caution*

CYP2C8	CYP2C9	CYP2C19	CYP3A**	
Amodiaquine	Acenocoumarol	Clopidogrel	Alfentanil ^{1,2}	Ergotamine ²
Cerivastatin	Celecoxib	Diazepam	Alpha-dihydroergocryptine ¹	Everolimus ¹
Repaglinide	Diclofenac	Esoprazole	Alprazolam	Felodipine ¹
Rosiglitazone	Glipizide	Lansoprazole	Amlodipine	Fentanyl ²
Torsemide	Irbesartan	Moclobemide	Aplaviroc	Fluticasone ¹
	Losartan	Omeprazole	Aprepitant ¹	Indinavir ¹
	Phenytoin ²	Pantoprazole	Aripiprazole	Lopinavir ¹
	Piroxicam	Phenobarbitone	Atorvastatin	Lovastatin ¹
	S-ibuprofen	Phenytoin ²	Boceprevir	Maraviroc ¹
	Sulfamethoxazole	Proguanil	Brecanavir	Midazolam ¹
	Tolbutamide	Rabeprazole	Brotizolam ¹	Nifedipine
	Torsemide	S-mephenytoin	Budesonide ¹	Nisoldipine
			Buspirone ¹	Nitrendipine
			capravirine	Perospirone ¹
			casopitant	Quinine
			Conivaptan ¹	Saquinavir ¹
			Cyclosporine ²	Sildenafil ¹
			Darifenacin ¹	Simvastatin ¹
			Darunavir ¹	Sirolimus ^{1,2}
			Diazepam	Telaprevir
			Diergotamine ²	Tipranavir ¹
			Diltiazem	Tolvaptan
			Ebastine ¹	Triazolam ¹
			Eletriptan ¹	Verapamil
			Eplerenone ¹	

*Table was compiled from the Indiana University School of Medicine’s “Clinically Relevant” table, a list by the United States Food and Drug Administration (FDA) fda.gov/Drugs/DevelopmentApprovalProcess/DevelopmentResources/DrugInteractionsLabeling/ucm080499.htm, and the University of Washington’s Drug Interaction Database.

¹ Sensitive substrates: Drugs whose plasma area under concentration-time curve (AUC) values have been shown to increase 5-fold or higher when co-administered with a potent inhibitor of the respective enzyme.

² Substrates with narrow therapeutic index (NTI): Drugs whose exposure-response indicates that increases in their exposure levels by the concomitant use of potent inhibitors may lead to serious safety concerns (e.g., TdP).

Table B: List of CYP450 Substrates to be used with Caution – CYP2B6

CYP2B6*
bupropion ¹
Cyclophosphamide
Efavirenz ¹
Ifosfamide
Methadone
Thiotepa
*Table was compiled from the Indiana University School of Medicine’s “Clinically Relevant” table, a list by the FDA (http://fda.gov/Drugs/DevelopmentApprovalProcess/DevelopmentResources/DrugInteractionsLabeling/ucm080499.htm) and the University of Washington’s Drug Interaction Database. ¹ Sensitive substrates: The area under the concentration-time curves (AUCs) of these substrates were not increased by 5-fold or more with a CYP2B6 inhibitor, but they represent the most sensitive substrates studied with available inhibitors evaluated to date.

Table C: Strong/moderate CYP3A4 Inhibitors and CYP3A4 Inducers to be Prohibited or Administered with Caution when Co-administered with Encorafenib

Strong Inhibitors (prohibited)	
boceprevir	nefazodone
Clarithromycin	Nelfinavir
Conivaptan	Posaconazole
Indinavir	Ritonavir
Itraconazole	Saquinavir
Ketoconazole	Telithromycin
Lopinavir	Troleandomycin
Telaprevir	Grapefruit juice (citrus paradisi fruit juice)
Mibefradil	Voriconazole
Moderate inhibitors (use with caution)	
Ciprofloxacin	Erythromycin
Fluconazole	Amprenavir
Verapamil	Imatinib
Atazanavir	Schisandra sphenanthera
Aprepitant	Casopitant
Cyclosporine	Cimetidine
Tofisopam	Dronedarone
Fosamprenavir	Darunavir
Diltiazem	
Strong Inducers (prohibited)	
Avasimibe	Rifampin
Carbamazepine	St. John’s wort
Phenytoin	
Moderate Inducers (prohibited)	
Bosentan	Efavirenz
Etravirine	Modafinil
Reproduced from fda.gov/Drugs/DevelopmentApprovalProcess/DevelopmentResources/DrugInteractionsLabeling/ucm080499.htm	

Table D: Substrates of BCRP, OCTs, OATs and OATPs to be administered with Caution

Substrates	
BCRP	Imatinib, irinotecan, lapatinib, methotrexate, mitoxantrone, rosuvastatin, sulfasalazine, topotecan
P-gp	Aliskiren, ambrisentan, colchicine, dabigatran etexilate, digoxin, everolimus, fexofenadine, imatinib, lapatinib, maraviroc, nilotinib, posaconazole, ranolazine, saxagliptin, sirolimus, sitagliptin, talinolol, tolvaptan, topotecan
OCT2	Amantadine, amiloride, cimetidine, dopamine, famotidine, memantine, metformin, pindolol, procainamide, ranitidine, varenicline, oxaliplatin
OAT1	Adefovir, captopril, furosemide, lamivudine, methotrexate, oseltamivir, tenofovir, zalcitabine, zidovudine
OAT3	Acyclovir, bumetanide, ciprofloxacin, famotidine, furosemide, methotrexate, zidovudine, oseltamivir acid, (the active metabolite of oseltamivir), penicillin G, pravastatin, rosuvastatin, sitagliptin
OATP1B1	Atrasentan, atorvastatin, bosentan, ezetimibe, fluvastatin, glyburide, SN-38 (active metabolite of irinotecan), rosuvastatin, simvastatin acid, pitavastatin, pravastatin, repaglinide, rifampin, valsartan, olmesartan
OATP1B3	Atorvastatin, rosuvastatin, pitavastatin, telmisartan, valsartan, olmesartan
Reproduced from fda.gov/Drugs/DevelopmentApprovalProcess/DevelopmentResources/DrugInteractionsLabeling/ucm080499.htm	

Table E: P-gp and BCRP Inhibitors/Inducers to be used with Caution

Transporter	Gene	Inhibitor ¹	Inducer ²
P-gp	ABCB1	Amiodarone, azithromycin, captopril, carvedilol, clarithromycin, conivaptan, cyclosporine, diltiazem, dronedarone, erythromycin, felodipine, itraconazole, ketoconazole, lopinavir and ritonavir, quercetin, quinidine, ranolazine, verapamil	Avasimibe, carbamazepine, phenytoin, rifampin, St John’s wort, tipranavir/ritonavir
BCRP	ABCG2	Cyclosporine, elacridar (GF120918), eltrombopag, gefitinib	Not known
Reproduced from fda.gov/Drugs/DevelopmentApprovalProcess/DevelopmentResources/DrugInteractionsLabeling/ucm080499.htm			
1. Inhibitors listed for P-gp are those that showed > 25% increase in digoxin area under the concentration-time curve (AUC) or otherwise indicated if substrate is other than digoxin.			
2. Inducers listed for P-gp are those that showed > 20% decrease in digoxin AUC or otherwise indicated if substrate is other than digoxin.			

Table F: List of Inhibitors of UGT1A1 to be used with Caution

Inhibitors of UGT1A1	atazanavir, erlotinib, flunitrazepam, gemfibrozil, indinavir, ketoconazole, nilotinib, pazopanib, propofol, regorafenib, sorafenib
----------------------	--

Table G: List of Potential QT Prolonging Drugs of Potential QT Prolonging Drugs¹

Drug	QT risk ²	Comment
Alfuzosin	possible risk	
Amantadine	possible risk	
Amiodarone	known risk	Females > Males, TdP risk regarded as low
Amitriptyline	conditional risk	Risk of TdP with overdosage. Substrate of CYP2C19
Arsenic trioxide	known risk	
Astemizole	known risk	No Longer available in U.S. Substrate for 3A4
Atazanavir	possible risk	
Azithromycin	possible risk	Rare reports
Bepidil	known risk	Females > Males
Chloral hydrate	possible risk	
Chloroquine	known risk	
Chlorpromazine	known risk	
Ciprofloxacin	conditional risk	Drug metabolism inhibitor- Risk for drug interactions
Cisapride	known risk	No longer available in the U.S.; available in Mexico. Substrate for 3A4
Citalopram	known risk	
Clarithromycin	known risk	Substrate for 3A4
Clomipramine	conditional risk	
Clozapine	possible risk	
Desipramine	conditional risk	Risk of TdP with overdosage
Diphenhydramine	conditional risk	Risk of QT increase/TdP in overdosages
Disopyramide	known risk	Females > Males
Dofetilide	known risk	
Dolasetron	possible risk	
Domperidone	known risk	Not available in the U.S.
Doxepin	conditional risk	
Dronedarone	possible risk	Substrate for 3A4
Droperidol	known risk	
Eribulin	possible risk	
Erythromycin	known risk	Females>Males. Substrate for 3A4
Escitalopram	possible risk	
Famotidine	possible risk	
Felbamate	possible risk	
Fingolimod	possible risk	
Flecainide	known risk	
Fluconazole	conditional risk	Drug metabolism inhibitor- Risk for drug interactions
Fluoxetine	conditional risk	
Foscarnet	possible risk	
Fosphenytoin	possible risk	
Galantamine	conditional risk	
Gatifloxacin	possible risk	
Gemifloxacin	possible risk	
Granisetron	possible risk	
Halofantrine	known risk	Females>Males
Haloperidol	known risk	When given intravenously or at higher-than- recommended doses, risk of sudden death, QT prolongation and torsades increases. Substrate for 3A4
Ibutilide	known risk	Females>Males
Imipramine	conditional risk	Risk of TdP in overdosage

Drug	QT risk ²	Comment
Indapamide	possible risk	
Isradipine	possible risk	
Itraconazole	conditional risk	Drug metabolism inhibitor- Risk for drug interactions
Ketoconazole	conditional risk	Drug metabolism inhibitor
Levofloxacin	possible risk	
Levomethadyl	known risk	Not available in the U.S.
Lithium	possible risk	
Mesoridazine	known risk	
Methadone	known risk	Females>Males. Substrate for 3A4
Moexipril/HCTZ	possible risk	
Moxifloxacin	known risk	
Nicardipine	possible risk	
Nortriptyline	conditional risk	
Octreotide	possible risk	
Ofloxacin	possible risk	
Ondansetron	possible risk	
Oxytocin	possible risk	
Paliperidone	possible risk	
Paroxetine	conditional risk	
Pentamidine	known risk	Females > Males
Perflutren lipid microspheres	possible risk	
Pimozide	known risk	Females > Males. Substrate for 3A4
Probuco	known risk	No longer available in U.S.
Procainamide	known risk	
Protriptyline	conditional risk	
Quetiapine	possible risk	Substrate for 3A4
Quinidine	known risk	Females > Males. Substrate for 3A4
Ranolazine	possible risk	
Risperidone	possible risk	
Ritonavir	conditional risk	Substrate for 3A4
Roxithromycin*	possible risk	*not available in the United States
Sertindole	possible risk	
Sertraline	conditional risk	
Solifenacin	conditional risk	
Sotalol	known risk	Females > Males
Sparfloxacin	known risk	
Tacrolimus	possible risk	Substrate for 3A4
Telithromycin	possible risk	Substrate for 3A4
Terfenadine	known risk	No longer available in U.S.Substrate for 3A4
Thioridazine	known risk	
Tizanidine	possible risk	
Trazodone	conditional risk	Substrate for 3A4
Trimethoprim-Sulfa	conditional risk	
Trimipramine	conditional risk	
Vandetanib	known risk	
Vardenafil	possible risk	Substrate for 3A4
Venlafaxine	possible risk	
Voriconazole	possible risk	
Ziprasidone	possible risk	

¹ Additional agents can be found at <https://www.crediblemeds.org>
² Classification according to the Qtdrugs.org Advisory Board of the Arizona CERT

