7.1. PROHIBITED THERAPY AND THERAPEUTIC/DIAGNOSTIC PROCEDURES

None of the concomitant therapies and therapeutic/diagnostic procedures listed below are allowed during the study period (except those listed in **Section 7.2**):

- Anticancer agents such as cytotoxic chemotherapy small-molecule targeted agents, biological agents, immune response modifiers or hormonal therapy,
- Local therapies which could interfere with treatment (e.g. surgical excision or ablation of lesions are not permitted without Sponsor approval while subjects are receiving study treatment),
- Investigational drugs (other than study drugs) and devices,
- Radiation therapy (not including palliative radiotherapy at focal sites that covers $\leq 10\%$ of the bone marrow reserve),
- Herbal preparations/medications. Subjects should stop using herbal medications 7 days prior to first dose of study treatment,
- Concomitant moderate or strong systemic CYP3A4 inhibitors or inducers which are likely to significantly increase or decrease respectively encorafenib exposure and thus should not be used during this study (see **Section 17.5**).

If another therapy and/or therapeutic / diagnostic procedure has to be prescribed in the interests of the subject's health, the decision to discontinue the subject from the study should be taken by the Investigator.

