7.2. AUTHORIZED THERAPY, THERAPEUTIC AND DIAGNOSTIC PROCEDURES

In general, the use of any concomitant medication/therapies deemed necessary for the care of the subject is permitted, unless otherwise specified. Additional information regarding concomitant medications/therapies is provided in the Investigator's Brochures for encorafenib and binimetinib and the cetuximab locally approved labelling.

Subjects receiving any of the medications listed in **Section 17.5** must be used with caution carefully monitored for potentiation of toxicity due to any individual concomitant medication and may require dose titration of the drug substance. Investigators should use caution when prescribing concomitant medications, as clinical experience with these compounds in subjects with cancer is often limited. Investigators should contact the Sponsor or designee when they are unsure whether a drug should be prescribed to a subject in the clinical study. All concomitant medications/therapies, transfusions, procedures and dietary supplements must be documented in the e-CRF.

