7.2.5. Permitted Concomitant Therapy requiring Caution and/or Action

7.2.5.1. *CYP and UGT Substrates and Inhibitors*

Encorafenib is a reversible inhibitor of CYP2B6, CYP2C9, CYP3A4 and UGT1A1. It is also a time-dependent inhibitor of CYP3A4. Likewise, binimetinib is also a reversible inhibitor of CYP2B6. Permitted medications to be used with caution in this study include those that are sensitive substrates of CYP2B6, CYP2C8, CYP2C9, CYP2C19, CYP3A4, and UGT1A1 or those substrates that have a narrow therapeutic index (Section 17.5).

There is a potential for encorafenib to induce CYP3A4, which may reduce the effectiveness of hormonal contraception methods. Therefore, the use of at least one form of non-hormonal contraception is required during participation in this study (See Section 5.3 for use of contraception methods required for this study). Caution should be used in subjects receiving concomitant treatment with other drugs that are substrates of CYP3A4 as the efficacy of these drugs could be reduced when administered with encorafenib.

Encorafenib has been identified in vitro to be metabolized by CYP3A4 and to a lesser extent by CYP2C19. The use of strong inhibitors of CYP3A4 is prohibited. Concomitant use of moderate

CYP3A4 inhibitors while on study should be avoided. If use of moderate CYP3A4 inhibitors is unavoidable and no alternatives are available, short-term use (≤ 30 days) following discussion with the Sponsor may be permitted with accompanying dose reduction to one-half of the encorafenib dose prior to use of moderate CYP3A4 inhibitors (or as close as can be achieved without exceeding the target dose). The encorafenib dose that was taken prior to initiating the CYP3A4 inhibitor may be resumed after the inhibitor has been discontinued for 3 to 5 elimination half lives. Strong inhibitors of CYP2C19 should be used with caution when co-administered with encorafenib.

Binimetinib has been identified to be primarily metabolized by glucuronidation. It is advised that strong inhibitors of UGT1A1 should be used with caution when co-administered with binimetinib (**Section 17.5**).

Subjects should be closely monitored for the occurrence of AEs.

7.2.5.2. *Transporter Substrate and Inhibitors*

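### Table C in Protocol 17.5 asks only for caution with moderate CYP3A4 inhibitors and omits the Section 7.2.5.1 conditions, including half-dose encorafenib

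*Protocol*

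**What the plan says.** Four places in the Protocol deal with moderate CYP3A4 inhibitors.

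- **Section 7.1** includes among therapies that are not allowed "Concomitant moderate or strong systemic CYP3A4 inhibitors or inducers". The same bullet describes them as drugs "which are likely to significantly increase or decrease respectively encorafenib exposure and thus should not be used during this study". It refers to Section 17.5. The opening sentence of the section exempts whatever Section 7.2 lists.
- **Section 7.2** gives the general permission: medication "deemed necessary for the care of the subject is permitted, unless otherwise specified". For drugs listed in Section 17.5 it asks for caution and monitoring and mentions possible dose titration. It does not say how much to titrate or for how long.
- **Section 7.2.5.1** states that strong inhibitors are prohibited and that moderate "CYP3A4 inhibitors while on study should be avoided". If use is unavoidable and there is no alternative, it may be permitted for up to 30 days after discussion with the Sponsor, with "dose reduction to one-half of the encorafenib dose prior to use of moderate CYP3A4 inhibitors". Where an exact half is not possible, the dose is to come as near to it as it can without going over. The earlier dose may resume once the inhibitor has been stopped for 3 to 5 elimination half-lives.
- **Section 17.5, Table C** names the drugs in four groups. Strong inhibitors and strong inducers are headed as prohibited, and so is the other moderate group: "Moderate Inducers (prohibited". The remaining group is headed "Moderate inhibitors (use with caution".

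**The concern.** Table C is where a site finds drug names, and Section 7.1 sends the reader to Section 17.5. For this one group the label drops every condition that Section 7.2.5.1 attaches to use, and nothing in the table leads back to that section. The general text of Section 7.2 also speaks of caution for Section 17.5 drugs, so a reader who goes from 7.1 to 7.2 to Table C meets consistent wording and has little reason to look further. The sentences on moderate inhibitors in Section 7.2.5.1 do not mention Table C either.

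What is at stake is encorafenib exposure in individual subjects. Section 7.1 itself says these drugs are likely to change it significantly. Section 1.2.1 reports that 9 of the first 34 subjects treated with single-agent encorafenib 450 mg in the dose-expansion phase had a dose-limiting toxicity in Cycle 1, and that 300 mg was then chosen as the recommended dose. The same section also reports that 450 mg with cetuximab did not reach a maximum tolerated dose. The documents do not quantify the rise in exposure caused by a moderate inhibitor.

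**Working it through.** No sample size, power or alpha figure is involved. The check sets the texts side by side and then follows one example through them.

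| Element | Section 7.2.5.1 | Section 7.2, general text on 17.5 drugs | Table C |
|---|---|---|---|
| Default position | Avoid | Caution | Caution |
| Only if unavoidable and no alternative | Yes | Not stated | Not stated |
| Time limit | 30 days | Not stated | Not stated |
| Sponsor discussion beforehand | Required | Only when the investigator is unsure | Not stated |
| Encorafenib dose | One-half of the prior dose | Titration mentioned, no amount | Not stated |
| Reference to Section 7.2.5.1 | n/a | None | None |

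**Which label is right for this group?** Section 7.1 bars moderate inhibitors but exempts what Section 7.2 lists, and Section 7.2.5.1 falls within 7.2. Read together, these mean: not to be used, except under the conditions of 7.2.5.1. A label other than prohibited is therefore correct for moderate inhibitors. The fault is that the label given is incomplete and weaker than the rule it stands for.

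**Example.** A subject takes encorafenib 300 mg daily (4 capsules of 75 mg) and the site considers fluconazole, which Table C lists as a moderate inhibitor.

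- Under Section 7.2.5.1, the site looks for an alternative. If there is none, it discusses the case with the Sponsor, gives fluconazole for at most 30 days and reduces encorafenib to 300 / 2 = 150 mg daily (150 / 75 = 2 capsules).
- From Table C alone, the site uses caution. It is told nothing about dose or duration, so encorafenib may stay at 300 mg with no end date for fluconazole.

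The daily dose given alongside the inhibitor would then be 300 / 150 = 2 times what Section 7.2.5.1 requires.

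**The case against.** The strongest reply is that the body of the protocol governs and is clear. Section 7.2 permits drugs only where nothing else is specified, and Section 7.2.5.1 does specify. The heading of 7.2.5 speaks of caution and action, so the Table C label can be read as shorthand for it. A site would have to rely on an appendix list and ignore the section that deals with these drugs. Exclusion criterion 6 already keeps moderate inhibitors out for the week before treatment, and Section 7.2 tells investigators to contact the Sponsor when unsure. Enrolment is complete: the last subject started treatment on 27 December 2019.

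Most of this stands, and it is why the point is minor. It does not remove the point. The shorthand keeps the caution and loses the action, which is a required dose cut. A plain caution label gives an investigator little reason to feel unsure. Exclusion criterion 6 does not cover drugs started during treatment. The study extension continues treatment at the same doses and schedule, so the wording still applies to some subjects.

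Three stronger readings are tempting, and the documents do not support them.

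- A reader might infer that Table C contradicts an outright ban in Section 7.1. It does not, because 7.1 carries the exemption for Section 7.2.
- A reader might infer that Table C directs sites to keep the full dose. It is silent on dose.
- A reader might infer that halving a dose already reduced to 225 or 150 mg breaches the 150 mg minimum. That minimum is stated in Section 6.5.4.1 and in a footnote to Table 14, both of which deal with dose changes for adverse events. Section 7.2.5.1 is the specific rule here, with its own rounding instruction and prior Sponsor discussion. A conflict is not established.

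**Conclusion.** The point holds as a minor patient-safety inconsistency. The Table C heading for moderate CYP3A4 inhibitors is weaker than the rule in Section 7.2.5.1, omits all of its conditions and does not refer to it. Its practical size is the omitted halving of encorafenib (300 mg instead of 150 mg daily in the example) and the omitted 30-day limit. It arises only where a site works from the list, or from the list and the general text of Section 7.2, without reaching Section 7.2.5.1. The documents give no number of subjects exposed to these drugs, and none is estimated here. There is no consequence for the primary endpoint, type I error or power.

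**What to change.** Change the Table C heading to: *Moderate inhibitors (systemic use: avoid; only under the conditions of Section 7.2.5.1, including half-dose encorafenib, at most 30 days and Sponsor discussion)*. The word systemic follows Section 7.1. The heading should not go on to declare topical use unrestricted, because Section 7.2.5.1 gives no such permission. Also add a reference to Section 7.2.5.1 in the CYP3A4 bullet of Section 7.1 and in the sentence of Section 7.2 that cites Section 17.5.

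The cost is one heading and two cross-references. Section 15.1 requires every protocol change to go through a signed amendment, so the change belongs in the next one, with a notice to sites that still have subjects on treatment. It adds no procedure and no new dosing rule.
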